6.2.4. Overall Survival

OS is defined as the time in months between randomization and death due to any cause. One interim analysis and a final analysis of overall survival will be performed. The first interim will be performed at the time of the final analysis of the MFS primary endpoint. The overall survival will be compared between treatment groups using a 2-sided stratified log rank test. Patients without an event date will be censored at the date of the last contact.

At the time of final analysis of OS, subgroup analyses will be conducted using the same analysis methods as for the subgroup analyses of MFS described in Section 6.6.

At the final analysis of OS, an additional confounding factor for the OS analysis may come from patients who choose to access commercial enzalutamide, combination of enzalutamide and leuprolide and other commercially available treatments for the patients. The sponsors may explore the effect of crossover and post-study systemic anticancer therapy using rankpreserving structural failure time model (RPSFTM), and the inverse probability of censoring weighting (IPCW) method if appropriate. Justifications, limitations and assumptions of RPSFTM (Robins & Tsiatis 1991) and IPCW (Robins & Finkelstein, 2000) methods will be adequately evaluated.

6.3. Other Secondary Efficacy Endpoint(s)

The following efficacy analyses will be performed for the ITT population. The resulting 2-sided p-values will be considered descriptive and no adjustment will be made for multiplicity. Treatment group comparisons will be between the combination arms of enzalutamide plus leuprolide versus placebo plus leuprolide and between enzalutamide monotherapy therapy versus placebo plus leuprolide unless otherwise specified.

6.3.1. Time to Distant Metastasis

The time to distant metastasis is defined as the time in months from randomization to the earliest objective evidence of distant soft tissue metastases or metastatic bone disease by BICR. Soft tissue disease including lymph nodes above the aortic bifurcation and outside the pelvis and any bone metastases will be counted as distant metastases.

The time to distant metastasis will be compared between treatment groups using a 2-sided stratified log-rank test.

For patients not known to have distant metastases at the time of the analysis data cutoff, time to distant metastasis will be censored at the date of the last adequate assessment (see Section 5.2.4) on or before the analysis data cutoff date. Patients who were randomized but later confirmed to have metastatic disease at enrollment or patients with no postbaseline tumor assessment information will be censored on the date of randomization. Patients who initiate cytotoxic chemotherapy, abiraterone acetate, hormonal agents, or nonradioactive bone-targeting agents and systemic radiopharmaceuticals for prostate cancer, or any antineoplastic therapy without evidence of metastasis will be censored at the last adequate assessment prior to initiation of such therapy. (Note: if distant metastasis occurs on the same date as the start of such therapy the distant metastasis will count as an event.) Additionally patients with distant metastasis after 2 or more missing tumor assessment will be censored at the last adequate assessments are assessed every 24 weeks. Therefore time without adequate assessment is defined as 49 weeks (allowing for a $\pm/-1$ week window for assessments).

6.3.2. Proportion of Patients Who Remain Treatment-Free at 2 Years After Suspension of Study Treatment

The proportion of patients per group who remain treatment-free 2 years after suspension of study treatment at week 37 due to undetectable PSA will be compared between treatment groups using the stratified Cochran-Mantel-Haenszel test. Two-sided 95% CIs per group will be reported using the Clopper-Pearson method. The differences in proportions between treatment groups and 95% CI using Wald method will be provided.

6.3.3. Proportion of Patients With Undetectable PSA at 2 Years

The proportion of patients per group with undetectable PSA 2 years after suspension of study treatment at week 37 due to undetectable PSA will be compared between treatment groups using the stratified Cochran-Mantel-Haenszel test. Two-sided 95% CIs per group will be reported using the Clopper-Pearson method. The differences in proportions between treatment groups and 95% CI using Wald method will be provided.

6.3.4. Proportion of Patients With Undetectable PSA at 36 Weeks

The proportion of patients per group with undetectable PSA at 36 weeks will be compared between treatment groups using the stratified Cochran-Mantel-Haenszel test. Two-sided 95% CIs per group will be reported using the Clopper-Pearson method. The differences in proportions between treatment groups and 95% CI using Wald method will be provided.

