10.4. Efficacy Analyses

All efficacy analyses will incorporate the randomization stratification by screening PSA ≤ 10 ng/mL versus > 10 ng/mL, PSA doubling time ≤ 3 months versus > 3 to ≤ 9 months, and by prior hormonal therapy versus no prior hormonal therapy, unless otherwise noted.

The analytical approach will be described in detail in the statistical analysis plan.

Patients who are randomized and later found to have metastatic disease at enrollment will be censored at randomization for time-to-event analyses. The statistical analysis plan will provide details for additional sensitivity analyses of selected endpoints.

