3.2.2. Other Secondary Endpoints

3.2.2.1. Time to distant metastasis

The time to distant metastasis is defined as the time in months from randomization to the earliest objective evidence of distant soft tissue metastases or metastatic bone disease by BICR. Soft tissue disease including lymph nodes above the aortic bifurcation and outside the pelvis and any bone metastases will be counted as distant metastases. Refer to Section 6.3.1 for details on censoring rules.

3.2.2.2. Proportion of patients who remain treatment-free 2 years after suspension of study treatment at week 37 due to undetectable PSA

The proportion of patients who remain treatment-free 2 years after suspension of study treatment at week 37 due to undetectable PSA is defined as number of patients remaining treatment-free 2 years after suspension of study treatment at week 37 due to undetectable PSA divided by the total number of patients with suspension of study drugs at week 37 due to undetectable PSA in each treatment group.

3.2.2.3. Proportion of patients per group with undetectable PSA 2 years after suspension of study treatments at week 37 due to undetectable PSA

The proportion of patients per group with undetectable PSA 2 years after suspension of study treatments at week 37 due to undetectable PSA is defined as number of patients with undetectable PSA 2 years after suspension of study treatments at week 37 due to undetectable PSA divided by the total number of patients with suspension of study drugs at week 37 due to undetectable PSA in each treatment groups.

3.2.2.4. Proportion of patients per group with undetectable PSA at 36 weeks on study drug

The proportion of patients per group with undetectable PSA at 36 weeks on study drug is defined asby the number of patients with undetectable PSA at 36 weeks divided by the total number of patients with PSA value at week 36 in each treatment group.

3.2.2.5. Time to resumption of any hormonal therapy following suspension at week 37 due to undetectable PSA

The time to resumption of any hormonal therapy following suspension at week 37 due to undetectable PSA is defined as the time in months between the date of treatment suspension at week 37 due to undetectable PSA and the date that hormonal therapy is restarted. Patients not starting hormonal therapy at the time of analysis will be censored at the date of last assessment before the analysis data cutoff date.

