5.2.12. Analyses for Time-to-Event Data

A 2-sided stratified log-rank test will be used for comparing treatments unless otherwise specified. Hazard ratios and the associated 95% 2-sided confidence intervals are estimated by stratified Cox proportional hazards models, including treatment as a covariate. Stratified analyses will utilize strata as defined in the randomization system unless otherwise specified. Unstratified analyses may be used in sensitivity analyses, subgroup analyses and supportive analyses, if applicable.

TTE endpoints will be summarized using the Kaplan-Meier method and estimated survival curves will be displayed graphically when appropriate. Graphs will describe the number of patients at risk over time. The median, quartiles, and probabilities of an event at particular points in time will be estimated by the Kaplan-Meier method. Confidence intervals for

medians and quartiles are based on the Brookmeyer-Crowley method. Confidence intervals for the estimated probability of event at a particular time point will be generated using the Greenwood's formula.

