6.3.5. Time to Resumption of any Hormonal Therapy

The time to resumption of any hormonal therapy is defined as the time in months between the date of treatment suspension at week 37 due to undetectable PSA and the date that hormonal therapy is restarted. The time to resumption of any hormonal therapy will be compared between treatment groups using a 2-sided log-rank test. Patients without observed resumption of any hormonal therapy at the time of analysis will be censored at the date of

last visit. A review of medication prior to unblinded will be performed to identify normal therapies.

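### Three response proportions are tested with the randomization strata, but their differences carry a Wald interval with no stratum weighting

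*SAP*

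**What the plan says.** SAP 6.3.4 gives the test as follows: "The proportion of patients per group with undetectable PSA at 36 weeks will be compared between treatment groups using the stratified Cochran-Mantel-Haenszel test". After exact Clopper-Pearson intervals for each group it adds: "The differences in proportions between treatment groups and 95% CI using Wald method will be provided". SAP 6.3.3 has the same structure for undetectable PSA two years after suspension. So does SAP 6.3.2, whose endpoint is not a PSA rate: "The proportion of patients per group who remain treatment-free 2 years after suspension of study treatment at week 37".

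For the two 2-year endpoints, SAP 3.2.2.2 and 3.2.2.3 take as denominator only the patients who suspended. The count is "divided by the total number of patients with suspension of study drugs at week 37 due to undetectable PSA in each treatment group".

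Protocol 10.4 sets the general rule: "All efficacy analyses will incorporate the randomization stratification by screening PSA", together with PSA doubling time and prior hormonal therapy, unless otherwise noted. Three two-level factors make 8 strata. SAP 6.3 classes the p-values for these endpoints as descriptive, without multiplicity adjustment.

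**The concern.** The test conditions on the strata. The effect reported beside it does not say that it does. No weights or pooling rule appear in 6.3.2 to 6.3.4. SAP 5.2.11, the general section on categorical data, gives one between-group interval (for the odds ratio), and it is built from the four cells of a single 2-by-2 table. The plain reading is therefore a crude difference with a crude Wald interval.

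Three things follow if screening PSA, PSA doubling time or prior hormonal therapy predict the outcome:

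- The interval is wider than the design allows.
- The interval can include zero while the CMH p-value is below 0.05.
- In 6.3.2 and 6.3.3 the compared groups are defined after randomization, so their stratum mix can differ by arm and move the crude difference itself.

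Because the p-values are descriptive, the difference and its interval are what readers will use most.

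**Working it through.** **The plan's own figures.** The documents give no sample size, power or expected rate for these endpoints. The nearest check is the primary design (SAP 5.1.1). Schoenfeld's formula gives 4(1.960 + 1.282)² / (ln 0.58)² = 141.6, that is 142 events for 90% power, as stated. The planned size of about 350 per arm comes from the same section. Everything below rests on assumed stratum sizes, rates and prognostic strength.

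**Interval width, closed form.** With stratum rates of mean p and standard deviation SD, the average within-stratum variance is p(1 − p) − SD². Hence

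stratified width / crude width = √(1 − SD² / [p(1 − p)]).

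- SD 0.05, p 0.70: √(1 − 0.0025/0.21) = 0.994.
- SD 0.15, p 0.85: √(1 − 0.0225/0.1275) = 0.907.

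**Interval width and agreement, simulated.** The simulation used 8 strata balanced between arms, 250 or 350 per arm, and 20,000 runs per setting. It compared the stratified CMH test, the crude Wald interval, and a Wald interval around the Mantel-Haenszel risk difference. One block of results, at 250 per arm:

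| Prognostic strength | Rates, control vs experimental | Half-width crude / stratified (points) | Width ratio | CMH disagrees with crude / stratified interval | Crude coverage |
|---|---|---|---|---|---|
| None | 81.8% vs 87.0% | 6.33 / 6.24 | 1.014 | 0.2% / 1.3% | 95.1% |
| Weak | 77.6% vs 83.7% | 6.89 / 6.73 | 1.023 | 0.4% / 1.8% | 95.1% |
| Moderate | 72.4% vs 79.3% | 7.46 / 7.13 | 1.046 | 1.7% / 1.9% | 95.3% |
| Strong | 66.9% vs 74.2% | 7.95 / 7.33 | 1.083 | 4.9% / 1.5% | 96.3% |

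Across all settings:

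- The width ratio runs from 1.01 to 1.08. The 1% at the bottom is a small-sample effect seen with non-prognostic strata, not a real gain.
- Crude coverage is 94.6% to 96.4%.
- Disagreement with CMH at 0.05 is 0% to 4.9% for the crude interval and 0.2% to 2.1% for the stratified one.

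In the strong row, CMH rejects in 48.1% of runs and the crude interval excludes zero in 43.2%. The gap of 4.9 points equals the whole disagreement rate, so there the test is significant while the crude interval covers zero.

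At 350 per arm with rates of 72.5% and 79.4%, the half-widths are 6.30 and 6.06 points (ratio 1.04). The crude value checks directly: 1.96 × √(0.725 × 0.275/350 + 0.794 × 0.206/350) = 6.31 points.

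**Shift in 6.3.2 and 6.3.3.** Let w be a stratum's share, r its probability of suspension in a given arm, and y its 2-year rate. The crude rate in that arm is Σ(w·r·y) / Σ(w·r). If y is the same in both arms within every stratum, the true within-stratum difference is zero. The crude difference is still generally non-zero when y varies between strata and the ratio of the arms' r values does too. With 8 strata and assumed week-36 response of 59% to 72% in control and 73% to 91% in the experimental arm, it came to −0.1 to −1.9 percentage points. CMH and a stratum-weighted difference remove this part. Neither removes other selection into the suspended subset.

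**The case against.** **Size.** The gain is small and conditional. No document shows that the strata are prognostic for these outcomes. A reader might infer that the Wald interval is invalid; the re-derived coverage says it is not. Lower coverage (93.6%) can be produced with rates of 2% and 1% in groups of 150 and 120, but neither those rates nor those sizes are in the documents. This objection stands, and it limits the point to precision and consistency.

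**The remedy does not guarantee agreement.** It does not. In the table, disagreement falls clearly only in the strong row and is higher than for the crude interval with no or weak prognostic effect. Stratified Newcombe and Miettinen-Nurminen intervals were not simulated. A crude difference also equals the difference of the two rates printed beside it, which a weighted one need not. This too stands.

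**Resumption of hormonal therapy.** A reader might infer from SAP 6.3.5 that an unstratified test is planned: "The time to resumption of any hormonal therapy will be compared between treatment groups using a 2-sided log-rank test". The text does not support that, because the word is only absent. SAP 5.2.12 sets the default: "A 2-sided stratified log-rank test will be used for comparing treatments unless otherwise specified". It confines the alternative: "Unstratified analyses may be used in sensitivity analyses, subgroup analyses and supportive analyses, if applicable". The protocol synopsis likewise names the stratified log-rank test for time-to-event endpoints. The SAP does write the qualifier out for pain and FACT-P, where the protocol has the same bare wording, so adding it in 6.3.5 would be tidy. A loss of power cannot be charged to an analysis that the plan does not state.

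**Timing.** Protocol 3.1 says that the primary analyses are complete and the study unblinded. The synopsis has secondary endpoints, apart from skeletal events, reported at the MFS analysis. SAP 5.1.2 does not list these three for update at the final OS analysis. A change of method now would come after unblinding, which affects how it should be labelled.

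**Conclusion.** The point holds as a minor improvement. In SAP 6.3.2 to 6.3.4 the test uses the randomization strata and the reported difference, as written, does not, although Protocol 10.4 asks efficacy analyses to incorporate them and no exception is noted. If the strata are prognostic, the crude interval is about 1% to 8% wider than a stratified one and can contradict the CMH result at 0.05 in up to about 5% of cases. In 6.3.2 and 6.3.3 the crude difference may also move, by up to about 2 percentage points under the inputs assumed above. All of these sizes depend on assumed stratum rates.

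The crude interval remains valid, and conservative when the strata matter. The endpoints are descriptive. No sample size, event count, power, alpha or formally tested conclusion is affected.

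**What to change.** In SAP 6.3.2, 6.3.3 and 6.3.4, specify the CMH-weighted (stratified) risk difference with a stratified 95% interval, for example stratified Newcombe or Miettinen-Nurminen, using the strata in the randomization system. Keep the crude proportions with their Clopper-Pearson intervals. Add a footnote that the weighted difference need not equal the difference of the crude rates.

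If the crude Wald differences have already been reported, keep them labelled as crude and descriptive, and present the stratified differences as supplementary analyses specified after unblinding.

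As an editorial clarification only, add the word stratified to SAP 6.3.5.

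The cost is a software option and a few lines of text. The two small downsides are the mismatch with the crude rates and that closer agreement with CMH can be expected only when the strata are clearly prognostic.

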6.3.5. Time to Resumption of any Hormonal Therapy

The time to resumption of any hormonal therapy is defined as the time in months between the date of treatment suspension at week 37 due to undetectable PSA and the date that hormonal therapy is restarted. The time to resumption of any hormonal therapy will be compared between treatment groups using a 2-sided log-rank test. Patients without observed resumption of any hormonal therapy at the time of analysis will be censored at the date of

last visit. A review of medication prior to unblinded will be performed to identify normal therapies.

6.3.6. Time to Castration Resistance

Time to castration resistance applies only to patients receiving leuprolide treatment and is defined as the time in months from randomization to the first occurrence of radiographic disease progression by BICR, PSA progression (as defined in Section 3.2.1) or symptomatic skeletal event whichever occurs first with castrate levels of testosterone (<50 ng/dL). The latest testosterone value measured prior to or at the date of radiographic disease progression by BICR, PSA progression or a symptomatic skeletal event is used to determine if the event is a castration resistance event.

Time to castration resistance is defined as the time in months from randomization to the first castration-resistant event (radiographic disease progression, PSA progression or symptomatic skeletal event), whichever occurs first. In patients with no documented castration resistance event, the time to castration resistance will be censored on the latest date from: the date of last radiographic assessment prior to the start of any new prostate cancer therapy, the last PSA sample taken prior to the start of any new prostate cancer therapy and prior to 2 or more consecutive missed PSA assessments (if applicable), and the last visit date performed. Patients with no baseline radiographic assessment, patients with no post baseline radiographic assessments, patients with all post-baseline radiographic assessments documented as "Not Evaluable", patients with no baseline PSA, and in patients with no postbaseline PSA results, the time to castration resistance will be censored on the date of randomization.

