7.2. Concomitant Therapy

Concomitant medications will be assessed at all clinic visits. All concomitant medications, including analgesic medications and opiates (including opioid-containing medications), must be recorded on the appropriate case report form. If the use of any medication during the study is due to an adverse event, the adverse event must be recorded on the adverse event case report form and in the patient's source documents.

Initiation of bisphosphonates or denosumab for the prevention of bone metastases is prohibited following randomization; however, treatment with these agents should continue at a stable dose if initiated at least 4 weeks before randomization. Initiation of bisphosphonates or denosumab at doses to treat osteoporosis is allowed if a diagnosis of osteoporosis is made during the study.

Patients are strongly encouraged to obtain an adequate intake of dietary calcium (at least 1000 mg per day, including supplements if necessary) and vitamin D (at least 800-1000 international units per day for adults 50 years of age and older) and to engage in regular exercise to maintain muscle strength and bone density.

Initiation of abiraterone or antiandrogen therapy is prohibited before radiographic disease progression.

Randomized study drug treatment must be permanently discontinued upon initiation of anti-cancer chemotherapy or antiandrogen therapy (eg, bicalutamide, nilutamide, or

flutamide). Note: Localized anticancer therapy (eg, topical treatment of non-melanoma skin malignancy, intravesical Bacillus Calmette-Guerin [BCG] treatment) may be acceptable upon prior Sponsor and Investigator agreement and written Sponsor approval.

Patients who discontinue study drug treatment due to initiation of any such therapy will remain in the study, complete safety follow-up per [Section 5.4](#), and then begin long-term follow-up assessments every 12 weeks thereafter based on the 12-week visit schedule determined at randomization per [Section 5.5](#).

The following treatments are allowed:

- Blood transfusions and growth factor support per standard of care and institutional guidelines;
- Corticosteroids for nonprostate cancer indication;
- Pain therapy per standard of care and institutional guidelines;
- Palliative procedures to treat skeletal-related events.

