3.2.2.6. Time to castration resistance

Time to castration resistance applies only to patients receiving leuprolide treatment and is defined as the time in months from randomization to the first occurrence of radiographic disease progression by BICR, PSA progression (as defined above in Section 3.2.1) or symptomatic skeletal event whichever occurs first with castrate levels of testosterone (<50 ng/dL). The latest testosterone value measured prior to or at the date of radiographic disease progression by BICR, PSA progression or a symptomatic skeletal event is used to

determine if the event is a castration resistance event. Refer to Section 6.3.6 for details on censoring rules.

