6.2.2. Time to PSA Progression

Only results from PSA samples taken before the initiation of any new prostate cancer therapy and after the start of study drug will be considered.

PSA progression is defined in Section 3.2.1 as the date that a \geq 25% increase and an absolute increase of \geq 2 µg/L (2 ng/mL) above the nadir (or baseline for patients with no PSA decline by week 25) that is confirmed by a second consecutive value at least 3 weeks later. The date of PSA progression is the first date the PSA progression is observed. For patients who have suspended treatment at week 37 and later reinitiated treatment, baseline will be defined as the last PSA assessment prior to or on the date of reinitiation. The date of PSA progression is the first date the PSA progression is observed.

PSA progression is only defined during active study treatment; therefore, patients meeting PSA progression during the suspension period will be censored unless the PSA progression criteria are subsequently met following treatment reinitiation. Time to PSA progression will be censored on the date of the last PSA sample taken. Patients with PSA progression after 2 or more consecutive missed PSA assessments (ie, time interval >6 months or 182 days between 2 consecutive PSA samples) will be censored on the date of last PSA assessment prior to the missed assessments. In patients with no baseline PSA and patients with no postbaseline PSA results, time to PSA progression will be censored on the date of randomization.

Time to PSA progression will be compared between treatment groups using a 2-sided stratified log-rank test.

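### Time to castration resistance is censored at the latest of three dates; the last visit date has no cut, so the cuts at new therapy and missed PSA assessments have almost no effect

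*SAP*

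**What the plan says.** Time to castration resistance is defined for patients receiving leuprolide. An event is the first of central-review radiographic progression, PSA progression or a symptomatic skeletal event, with castrate testosterone (SAP 3.2.2.6 and 6.3.6). For patients without an event, SAP 6.3.6 states that "the time to castration resistance will be censored on the latest date from: the date of last radiographic assessment prior to the start"; it then continues, so that three dates compete and the latest is taken:

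- the last scan, restricted: "the date of last radiographic assessment prior to the start of any new prostate cancer therapy";
- the last PSA sample, restricted to before new therapy "and prior to 2 or more consecutive missed PSA assessments (if applicable");
- the last visit, unrestricted: "and the last visit date performed".

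No other section limits the third date. SAP 3.2.2.6 says only "Refer to Section 6.3.6 for details on censoring rules", and protocol 10.4.3.7 gives no censoring rule.

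Follow-up does not end at new therapy. Protocol 7.2 states: "Patients who discontinue study drug treatment due to initiation of any such therapy will remain in the study". Protocol 5.5 schedules long-term follow-up every 12 weeks.

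For PSA progression, SAP 6.2.2 states: "Only results from PSA samples taken before the initiation of any new prostate cancer therapy and after the start of study drug will be considered".

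**The concern.** The authors wrote two cuts, so they evidently meant follow-up for this endpoint to stop at new therapy and at a gap in PSA testing. Taking the maximum of two restricted dates and one later unrestricted date returns the unrestricted one.

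The extra time is only partly observed. PSA values after new therapy cannot produce a PSA progression event. The long-term follow-up procedures in protocol Table 9 list neither PSA nor testosterone, so the castrate-level test would rest on an older value. One of the three components is switched off while the patient stays in the risk set.

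The rule also differs from its neighbours. MFS (SAP 6.1.1.1) and time to distant metastasis (6.3.1) censor at the last adequate assessment before new therapy, and time to PSA progression (6.2.2) censors before the gap in testing. In those analyses the cuts take effect.

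At stake are the event-free rates and the hazard ratio for the two leuprolide arms.

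**Working it through.** **Step 1. Which date wins.** The inputs are visits every 12 weeks, scans every 24 weeks, study day = (week − 1) × 7 + 1, and 30.4375 days per month (SAP 5.2.6). The patient dates are illustrative.

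- *New therapy.* Last scan and PSA are at week 97, day 673; new therapy follows and visits continue. If the last visit is week 109, 121, 145 or 193, the rule gives day 757, 841, 1009 or 1345. With the cut in force the date would be day 673. The excess is 84, 168, 336 or 672 days; divided by 30.4375, that is 2.8, 5.5, 11.0 or 22.1 months.
- *PSA gap.* The last PSA before the gap is at week 61, day 421, with no new therapy. If the last visit is week 97, 121 or 145, the rule gives day 673, 841 or 1009, which is 8.3, 13.8 or 19.3 months after the PSA cut date.

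Protocol 5.2.1 lets procedures be split across the visit window, so a scan can fall shortly after the visit. In simulated schedules with scans 0, up to 5 or up to 14 days from the visit, the last visit set the date in 100% of cases once there was at least one visit after new therapy. Compared with a rule with no cuts at all, the cuts moved the censoring date by at most 14 days.

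**Step 2. What this does to the hazard ratio.** Let s be the share of the event hazard due to PSA progression, and π(t) the proportion of patients still at risk at time t who have started new therapy. If only PSA events are lost after new therapy, and new therapy is independent of event risk, then

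HR(t) = true HR × [1 − s·π_active(t)] / [1 − s·π_control(t)].

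The ratio moves toward 1 when π_control exceeds π_active and s > 0. There is no bias when s = 0. None of these quantities is in the documents.

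Worked example: event hazard 0.012 per month in control and 0.0048 in active (HR 0.40), new-therapy hazards 0.008 and 0.004, s = 0.5, t = 48 months.

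- Control, at risk without new therapy: exp(−0.020 × 48) = 0.383.
- Control, at risk on new therapy: 0.008/(0.008 + 0.006) × [exp(−0.006 × 48) − 0.383] = 0.571 × (0.750 − 0.383) = 0.210.
- Control event-free rate: 0.383 + 0.210 = 0.593, against a true exp(−0.012 × 48) = 0.562. So π_control = 0.210/0.593 = 0.354.
- Active, by the same formula: 0.656 + 0.625 × (0.891 − 0.656) = 0.656 + 0.147 = 0.803. So π_active = 0.147/0.803 = 0.183.
- HR at month 48: 0.40 × (1 − 0.092)/(1 − 0.177) = 0.44. It starts at 0.40 at randomization, so the averaged HR lies between the two.

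**Step 3. Simulation.** 20,000 patients per arm, control hazard 0.012 per month, true HR 0.40, follow-up 40–80 months. New-therapy hazards (control/active) were 0.004/0.002, 0.008/0.004 and 0.012/0.004, so that about 15%, 28% and 38% of controls start new therapy before an event. Ranges span the three scenarios.

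| PSA share (assumed) | HR, rule as written | Control 48-month event-free rate (true 56%) |
|---|---|---|
| 20% | 0.40–0.42 | 57–58% |
| 50% | 0.41–0.45 | 58–61% |
| 100% | 0.43–0.53 | 60–66% |

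Two alternatives under the same settings:

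- One cut at new therapy for both events and censoring: HR 0.40–0.41.
- Earlier censoring date only, with scan and skeletal events after new therapy still counted: HR about 0.36–0.39 at shares of 20–50% (as low as 0.35 on a repeat in the most unbalanced scenario). The control 48-month rate falls to 55–52% at a 50% share.

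**The case against.** **Scan and skeletal events still count after new therapy.** SAP 6.3.6 does not exclude them. Scans continue until centrally confirmed progression (protocol 5.5), and skeletal events are recorded at each follow-up visit. This stands. A reader might infer that all follow-up after new therapy is empty and take an HR of 0.43–0.53 as the expected distortion. That figure needs every event after new therapy to be lost, which the text does not say.

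**The PSA exclusion sits in 6.2.2, whereas 6.3.6 cites 3.2.1.** This is true but changes little. SAP 3.2.1.2 also confines PSA progression to time on study treatment, and protocol 7.2 requires study drug to stop at chemotherapy or antiandrogen therapy.

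**The last visit is a sensible date for skeletal events.** SAP 6.3.8 uses it for that endpoint, which may explain why it appears here. It does not make the two cuts work.

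**The last visit is undefined.** Follow-up may be by telephone or record review (protocol 5.5). If only clinic visits count, the visit date would win less often. This stands as an uncertainty and is itself a reason to define the term.

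**The rule does not flatter enzalutamide.** A reader might infer that it does. In every scenario examined the HR moved toward 1. It would move the other way only if new therapy started sooner in the combination arm.

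**The consequence is low and the analysis has probably been done.** SAP 6.3 makes the p-value descriptive. The synopsis places this endpoint with the primary MFS analysis, which protocol 3.1 reports as completed. Both facts stand. They lower the stakes and raise the cost of a change, but do not remove the error.

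**Conclusion.** As written, the censoring rule defeats its own restrictions. The visit date normally decides, and the cuts at new therapy and at missed PSA assessments shift the date by days at most. This follows from the text and the visit schedule, provided follow-up contacts count as visits.

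The size of the bias is uncertain and probably modest. It depends on the PSA share of events, the difference between arms in starting new therapy, and the independence of new therapy from event risk; all three are assumptions here. If controls start new therapy sooner, event-free rates are too high and the HR is pulled toward 1, by an amount between nothing and the 100% row of the table.

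A reader might carry this over to the trial's main conclusions. The documents do not support that: MFS and the alpha-protected key secondary endpoints have their own censoring rules, and this endpoint is descriptive.

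**What to change.** Apply one cut to both events and censoring:

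- Count a castration-resistance event only if it occurs on or before the start of new prostate cancer therapy and not after two or more consecutive missed PSA assessments.
- Censor all other patients at the last scan, PSA sample or visit before the earliest of new therapy, that gap, and data cutoff.
- Define which contacts count as a visit.
- Leave the separate rule on censoring at randomization unchanged.

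Do not simply delete the visit date or move the censoring date alone. Events after new therapy would still count while event-free patients left early, which exaggerates benefit.

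The price is that scan and skeletal events after new therapy are dropped, and censoring at new therapy may be informative. Keep an analysis that counts all events regardless of new therapy as a sensitivity analysis, parallel to MFS Sensitivity 1 in SAP 6.1.1.3.

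The wording and programming changes are small. Because the endpoint was due with the completed primary analysis, this is now a post hoc re-analysis of unblinded data. The study report should say which rule was programmed and present the corrected analysis, labelled as such, beside the result already produced.
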